9.2.5. Criteria for Assessing Local Tolerance

Secondary assessments of local tolerance will be based on Dermatologist and Subject self-assessment scores at each visit and reported adverse events. The baseline for these assessments will be defined as the assessments made 60±15 minutes after the facial peel procedure, before any test product application.

9.2.6. Handling of Dropouts and Missing Data

Missing data will not be imputed. All data available for dropouts will be considered in analyses.

9.3. Statistical Methods and Analytical Plan

Additional details of the proposed statistical analysis will be documented in the statistical analysis plan (SAP), which will be written following finalization of the protocol and prior to study unblinding / analysis (as appropriate).

9.3.1. Demographic and Baseline Characteristics

Age will be summarized descriptively for each product group using means, medians and standard deviations. Race, gender, Fitzpatrick phototype and Glogau photoaging type will be summarized by product group using frequency counts and percentages.

9.3.2. Primary Analysis(es)

Descriptive statistics (N, %, 95% confidence intervals) will be used to summarize the proportion of subjects in each product group with a favorable Evaluator global assessment of tolerance. The proportions may also be compared between product groups using Chi-square test, and difference in proportion and 95% confidence interval.

9.3.3. Secondary Analysis(es)

Changes from baseline in the Evaluator, Subject self-assessment and instrumental endpoints will be tabulated by product group and summarized descriptively using means, standard deviations and 95% confidence intervals and assessed for significance (different from zero) using t-tests or Wilcoxon signed rank tests dependent upon the distribution of the data.

 GlaxoSmithKline	Document Name	GSK267237/21308F 20 Day Cream.doc		
	Type	Version	Document Identifier	Effective Date
	eldo controlled	0.0; Current Effective Date: 07-Jun-2017 01:32:30	090032d580e2d8a6	07-Jun-2017 01:32:30
	Reason For Issue	Auto Issue		

Differences between product groups in the mean changes from baseline in Evaluator, Subject self-assessment and instrumental endpoints will also be explored using t-tests or Wilcoxon rank sum tests and summarised using 95% confidence intervals.

9.3.4. Safety Analysis(es)

Adverse events will be tabulated by product group and listed for inspection.

10. STUDY GOVERNANCE CONSIDERATIONS

10.1. Posting of Information on Publicly Available Clinical Trials Registers

Study information from this protocol will be posted on publicly available clinical trial registers before enrollment of subjects begins.

10.2. Regulatory and Ethical Considerations, Including the Informed Consent

The study will be conducted in accordance with all applicable regulatory requirements, and with GSK policy.

The study will also be conducted in accordance with ICH Good Clinical Practice (GCP), all applicable subject privacy requirements, and the guiding principles of the current version of the Declaration of Helsinki. This includes, but is not limited to, the following:

- Before initiating a trial, the investigator/institution should have written and dated approval/favorable opinion from the IEC for the trial protocol (including amendments), written informed consent form, consent form updates, subject recruitment procedures (e.g., advertisements), investigator brochure/ safety statement (including any updates) and any other written information to be provided to subjects. A letter or certificate of approval will be sent by the investigator to the sponsor prior to initiation of the study, and also when subsequent amendments to the protocol are made.
- Signed informed consent to be obtained for each subject before participation in the study (and for amendments as applicable)
- Investigator reporting requirements (e.g. reporting of AEs/SAEs/protocol deviations to IEC)
- GSK will provide full details of the above procedures, either verbally, in writing, or both.

 GlaxoSmithKline	Document Name	GSKCH 2017/2018 eCRF 20 Day Cream.doc		
	Type	Version	Document Identifier	Effective Date
	eldo_controlled	0.0: Current Effective Document	090032d580e2d8a6	07-Jun-2017 01:32:30
	Reason For Issue	Auto Issue		

10.3. Quality Control (Study Monitoring)

In accordance with applicable regulations including GCP, and GSK procedures, GSK or designee (i.e. third party vendor) monitors will contact the site prior to the start of the study to review with the site staff the protocol, study requirements, and their responsibilities to satisfy regulatory, ethical, and GSK requirements.

When reviewing data collection procedures, the discussion will include identification, agreement and documentation of data items for which the eCRF will serve as the source document.

GSK or designee will monitor the study and site activity to verify that the:

- Data are authentic, accurate, and complete.
- Safety and rights of subjects are being protected.
- Study is conducted in accordance with the currently approved protocol and any other study agreements, GCP, and all applicable regulatory requirements.

The extent and nature of monitoring will be described in a written monitoring plan on file at GSKCH. The investigator (or designee) agrees to allow the monitor direct access to all relevant documents and agrees to co-operate with the monitor to ensure that any problems detected in the course of these monitoring visits are resolved.

10.4. Quality Assurance

To ensure compliance with GCP and all applicable regulatory requirements, GSK may conduct a quality assurance assessment and/or audit of the site records, and the regulatory agencies may conduct a regulatory inspection at any time during or after completion of the study.

In the event of an assessment, audit or inspection, the investigator (and institution) must agree to grant the advisor(s), auditor(s) and inspector(s) direct access to all relevant documents and to allocate their time and the time of their staff to discuss the conduct of the study, any findings/relevant issues and to implement any corrective and/or preventative actions to address any findings/issues identified.

The sponsor will be available to help investigators prepare for an inspection.

10.5. Conditions for Terminating the Study

Upon completion or premature discontinuation of the study, the GSKCH monitor will conduct site closure activities with the investigator or site staff, as appropriate, in accordance with applicable regulations including GCP, and GSKCH Standard Operating Procedures.

 GlaxoSmithKline	Document Name	GSKCH 2017/2018 SF 20 Day Cream.doc		
	Type	Version	Document Identifier	Effective Date
	eldo_controlled	0.0: Discontinued/Effective/Current/Reviewed	090032d580e2d8a6	07-Jun-2017 01:32:30
	Reason For Issue	Auto Issue		

Both GSKCH and the Investigator reserve the right to temporarily suspend or prematurely discontinue this study at any time for reasons including, but not limited to, safety or ethical issues or severe non-compliance. For multicenter studies (if applicable), this can occur at one or more or at all sites.

If the trial is prematurely terminated or suspended for any reason, the investigator site should promptly inform the trial subjects and should assure appropriate therapy/ follow-up for the subjects. Where required by the applicable regulatory requirements, GSKCH should inform the regulatory authority(ies).

In addition:

1. If the investigator terminates or suspends a trial without prior agreement of GSKCH, the investigator site should promptly inform the sponsor and the IEC, and should provide the sponsor and the IEC a detailed written explanation of the termination or suspension.
2. If the GSKCH terminates or suspends a trial, the investigator should promptly inform the IEC and provide the IEC a detailed written explanation of the termination or suspension.
3. If the IEC terminates or suspends its approval/favorable opinion of a trial, the investigator should promptly notify the GSKCH and provide GSKCH with a detailed written explanation of the termination or suspension.

10.6. Records Retention

Following closure of the study, the investigator must maintain all site study records (except for those required by local regulations to be maintained elsewhere), in a safe and secure location.

The records (study/ site master file) must be maintained to allow easy and timely retrieval, when needed (e.g., for a GSK audit or regulatory inspection) and must be available for review in conjunction with assessment of the facility, supporting systems, and relevant site staff.

Where permitted by local laws/regulations or institutional policy, some or all of these records can be maintained in a format other than hard copy (e.g., microfiche, scanned, electronic); however, caution needs to be exercised before such action is taken.

The investigator must ensure that all reproductions are legible and are a true and accurate copy of the original and meet accessibility and retrieval standards, including re-generating a hard copy, if required. Furthermore, the investigator must ensure there is an acceptable back-up of these reproductions and that an acceptable quality control process exists for making these reproductions.

 GlaxoSmithKline	Document Name	eCRF 20 Day Cream.doc		
	Type	Version	Document Identifier	Effective Date
	eldo_controlled	0.0: Current Effective	090032d580e2d8a6	07-Jun-2017 01:32:30
	Reason For Issue	Auto Issue		

The investigator must assure that the subject’s anonymity will be maintained. On eCRFs or other documents submitted to GSKCH, subjects should not be identified by their names or initials, but by an identification code. The investigator should keep a separate log of subjects’ codes, names and addresses. Documents not for submission to GSKCH, e.g. subjects’ written consent forms, should be maintained by the investigator in strict confidence.

GSK will inform the investigator of the time period for retaining these records to comply with all applicable regulatory requirements (GSKCH recommends that documents be kept for 10 years). The investigator is also required to keep subject identification codes on file for at least 15 years after completion or discontinuation of the study. The minimum retention time will meet the strictest standard applicable to that site for the study, as dictated by any institutional requirements or local laws or regulations, GSK standards/procedures, and/or institutional requirements.

No study document should be destroyed without a prior written agreement between GSKCH and the investigator. The investigator must notify GSK of any changes in the archival arrangements, including, but not limited to, archival at an off-site facility or transfer of ownership of the records in the event the investigator is no longer associated with the site.

10.7. Provision of Study Results to Investigators, posting of Information on Publicly Available Clinical Trials Registers and Publication

Where required by applicable regulatory requirements, an investigator signatory will be identified for the approval of the clinical study report. The investigator will be provided reasonable access to statistical tables, figures, and relevant reports and will have the opportunity to review the complete study results at a GSK site or other mutually-agreeable location.

GSK will also provide the investigator with the full summary of the study results. The investigator is encouraged to share the summary results with the study subjects, as appropriate.

The procedures and timing for public disclosure of the results summary and for development of a manuscript for publication will be in accordance with GSK Policy.

A manuscript will be progressed for publication in the scientific literature if the results provide important scientific or medical knowledge.

 GlaxoSmithKline	Document Name	Gsk 207210721088F 20 Day Cream.doc		
	Type	Version	Document Identifier	Effective Date
	eldo_controlled	0.0: CURRENT/Effective/Current	090032d580e2d8a6	07-Jun-2017 01:32:30
	Reason For Issue	Auto Issue		

12. APPENDICES

12.1. Appendix 1 - Abbreviations and Trademarks

Abbreviations

AE	Adverse Event
AHA	Alpha Hydroxy Acid
ANVISA	Agência Nacional de Vigilância Sanitária
CD	Compact Disc
eCRF	Electronic Case Report Form
EDC	Electronic Data Capture
EEMCO	Efficacy Measurement of Cosmetics and Other Topical Products
g	Grams
GA	Glycolic Acid
GCP	Good Clinical Practice
GSKCH	GlaxoSmithKline Consumer Healthcare
h	Hours
ICH	International Conference on Harmonization of Technical Requirements for Registration of Pharmaceuticals for Human Use
ICF	Informed Consent Form
IEC	Independent Ethics Committee
ITT	Intention to Treat
LSLV	Last-Subject, Last Visit
MedDRA	Medical Dictionary for Regulatory Activities
min	Minutes
OTC	Over the Counter
PII	Personally Identifiable Information
PP	Per Protocol
SAE	Serious Adverse Event
SAP	Statistical Analysis Plan
SPF	Sun Protection Factor
TEWL	Transepidermal Water Loss
TMF	Trial Master File
UV	Ultraviolet

Trademark Information

Trademarks of the GlaxoSmithKline group of companies:
Physiogel
SunMax

 GlaxoSmithKline	Document Name	Est 200721072108F 20 Day Cream.doc		
	Type	Version	Document Identifier	Effective Date
	eldo controlled	0.0; CURRENT Effective Date: CURRENT	090032d580e2d8a6	07-Jun-2017 01:32:30
	Reason For Issue	Auto Issue		

Trademarks not owned by the GlaxoSmithKline group of companies:
Simple

12.2. Appendix 2 - Fitzpatrick Skin Type

Type	Description
I	Always burns, never tans
II	usually burns, tans minimally
III	sometimes mild burn, tans uniformly (cream white; fair with any hair or eye color)
IV	burns minimally, always tans well (moderate brown)
V	very rarely burns, tans very easily (dark brown)
VI	Never burns, never tans (deeply pigmented dark brown to darkest brown)

12.3. Appendix 3 - Glogau Photoaging Scale

Group	Classification	Skin Characteristics
I	Mild	Early Photoaging: mild pigment changes, no keratosis, minimal wrinkles, minimal or no makeup
II	Moderate	Early to Moderate Photoaging: Early brown spots visible, keratosis palpable but not visible, parallel smile lines begin to appear, wears some foundation
III	Advanced	Advanced Photoaging: Obvious discolorations, visible capillaries (telangiectasias), visible keratosis, wears heavier foundation always
IV	Severe	Severe Photoaging: Yellow-gray skin color, prior skin malignancies, wrinkles throughout - no normal skin, cannot wear makeup because it cakes and cracks

12.4. Appendix 4 - Exclusion Criteria for Review at Visit 2 and 3

1. PREGNANCY
Women who are known to be pregnant or who are intending to become pregnant over the duration of the study.

2. BREAST-FEEDING
Women who are breast-feeding.

 GlaxoSmithKline	Document Name	090032d580e2d816 20 Day Cream.doc		
	Type	Version	Document Identifier	Effective Date
	eldo_controlled	0.0; CURRENT Effective Date: CURRENT	090032d580e2d816	07-Jun-2017 01:32:30
	Reason For Issue	Auto Issue		

3. CONCURRENT MEDICATION/ MEDICAL HISTORY

A. Active skin disease or open wound in the test area.
 
E. Moles, tattoos, scars, irritated skin, hairs, etc. at the test area that could influence the investigation.

CONFIDENTIAL

**AMENDMENT #1 to STATISTICAL ANALYSIS PLAN FOR
PROTOCOL 207213**

A randomized, evaluator-blind, single-center and two-arm clinical study designed to evaluate the local tolerance and cosmetic efficacy of a topical skin care formulation in healthy female subjects with moderate to advanced photo-damaged facial skin who have undergone a 70% Glycolic Acid facial peel procedure

BIostatISTICS DEPARTMENT

GLAXOSMITHKLINE CONSUMER HEALTHCARE

PPD

Principal Biostatistician, Biostatistics

inVentiv Health Clinical

Final Version 2.0

15th August 2017

Timing for Amendment:

Before unblinding

After unblinding

SAP text:

Reason for Amendment:

- 1) Description for the analyses of individual scores at end of section 8.2 “Secondary Analysis”:

“If sufficient data is not available for formal analyses for individual scores, summary stats and frequency counts will be presented.”

- 2) Description for a figure for dermatologist total score at end of section 8.1 “Primary Analysis”:

“To visually inspect the treatment effect on dermatologist total score, a plot across time with the raw means will be produced. The plot will display a different symbol for each treatment group.”

- 3) Description for a figure for subject self-assessment total scores at end of section 8.2 “Secondary Analysis”:

“To visually inspect the treatment effect on subject self-assessment total scores, a plot across time with the raw means will be produced. The plot will display a different symbol for each treatment group.”

The following listing will be produced for the topline summary:

Listing No.	Description
2.1	Adverse Events – Safety Population

Appendix 2 List of Tables, Figures & Listings

Reason for Amendment:

Additional figures will be created:

Figures No.	Table Title (including population)	Template
9.3.2.1	Subject Self-Assessment Scores – Total Score - Safety Population	Figure 9.3.3.1
9.3.3.1	Dermatologist Assessment Scores – Total Score - Safety Population	Appendix 3

[figure not shown]
Appendix 3 Templates for Tables, Figures & Listings

Reason for Amendment:

Protocol No. 207213

Page x of y
Program Run Date:xxxx

Figure 9.3.3.1
Dermatologist Assessment Scores - Total Score
Safety Population

* = Significant difference from baseline (p < 0.05)

= Significant difference from baseline between groups

Note: No statistical comparison between pre-procedure assessment and baseline total scores was made

Program file name xxxxxxxxxxxxxxxxxxxxxxx

**Programmers Note: Figure to be created for Safety population. Same format for figures 9.3.2.1
Change the title, footnote and time points to match protocol.**

Table of Contents

Glossary	7
1 Introduction	8
2 Objectives.....	8
3 Study Design	8
4 Sample Size Determination	9
5 Data Considerations.....	10
5.1 Analysis Populations.....	10
5.2 Subgroups/Stratification	11
5.3 Time Windows.....	11
5.4 Missing Data Handling.....	11
6 Demographics and Baseline Characteristics	11
6.1 Subject Disposition.....	11
6.2 Demographics	11
7 Treatment Compliance and Concomitant Medications	12
7.1 Treatment Compliance.....	12
7.2 Concomitant Medications	12
8 Analysis	12
8.1 Primary Analysis.....	12
8.2 Secondary Analysis	13
8.3 Other Analyses	14
9 Safety Analysis.....	14
10 Interim Analysis	15
11 Topline Summary	15
12 Changes to Planned Analysis	15
13 References	15
Appendix 1 Study Schedule	16

Appendix 2 List of Tables, Figures & Listings	19
Appendix 3 Templates for Tables, Figures & Listings	22

Glossary

AE	Adverse Event
CI	Confidence Interval
ITT	Intent-to-Treat
MedDRA	Medical Dictionary for Regulatory Activities
PP	Per Protocol
TEAE	Treatment Emergent Adverse Event
TEWL	Transepidermal Water Loss

1 Introduction

This document describes the statistical methods and data presentations to be used in the summary and analysis of the final data from Protocol 207213.

2 Objectives

Objective(s)	Endpoint(s)
Primary	
Assessment of the local tolerance of the test product in subjects who have undergone a 70% Glycolic Acid facial peel	Evaluator (Dermatologist) global assessment of tolerance
Secondary	
Assessment of skin recovery (change from baseline) over a period of 14 days in subjects who have undergone a 70% Glycolic Acid facial peel	Combined (sum of) Evaluator (Dermatologist) scores for signs/symptoms of erythema, edema, desquamation and dryness
	Individual Evaluator (Dermatologist) scores for erythema, edema, desquamation and dryness
	Combined (sum of) subject self-assessment scores for redness, pain, stinging/burning, itching, tightness and dryness
	Individual subject self-assessment scores for redness, pain, stinging/burning, itching, tightness and dryness
	Instrumental measurement of barrier function (Tewameter) and moisturisation (Corneometer)
Subject global self-assessment	
Assessment of skin recovery (change from baseline) between treatment groups.	All assessments and measurements listed above

3 Study Design

- Evaluator-blind

- Single study center
- Parallel-group
- Healthy female subjects with moderate to advanced photo-damaged facial skin
- Single test product (Physiogel Calming Relief SPF 20 Cream) used in combination with commercial sunscreen (“washout product”, Sunmax Sensitive SPF 50). All subjects were to use the commercial sunscreen and cleanser provided. Randomization was to two groups (test product, no test product) with product usage as shown in the table below:

Randomized Group	Morning	Lunchtime*	Evening
Group 1 (Test product)	1. Cleansing 2. Test Product 3. Sunscreen	1. Sunscreen	1. Cleansing 2. Test Product
Group 2 (No test product)	1. Cleansing 2. Sunscreen	1. Sunscreen	1. Cleansing

*Lunchtime application must be at least 3 hours after previous sunscreen application

4 Sample Size Determination

Approximately 130 healthy females within the ages of 30 and 60 years (inclusive) with Fitzpatrick Skin Classification II-IV and moderate to advanced photo-damaged skin will be screened to randomize 80 subjects to ensure approximately 60 subjects (30 subjects per group) successfully complete the study.

The sample size is based on clinical considerations and literature precedent [Narurkar, Schalka, Sulimovic, Kim]. With 30 subjects per treatment group, a change from baseline in Transepidermal Water Loss (TEWL) at least half the magnitude of the standard deviation (e.g. assume $std=4$ (ref. RH02030 after 2D strip), and 2.1 point mean change from baseline) can be detected at two-sided $\alpha=0.05$ with 80% power.

5 Data Considerations

5.1 Analysis Populations

- All randomized subjects with at least one application of product in the test phase (i.e. test product for subjects randomized to receive test product (i.e. in Group 1) or sunscreen for subjects randomized not to receive test product (i.e. in Group 2)) will be included in the Safety population. Evaluator global assessment of tolerance, evaluator individual and subject individual assessments of tolerance and AE reporting will be based on the Safety population.
- All subjects in the safety population with at least one post-baseline efficacy (TEWL or corneometry) assessment will be included in the ITT population. All efficacy analyses will be based on the ITT population
- All subjects will be considered eligible for a Per Protocol (PP) population if they were randomized, received at least one application of product, had at least one post-procedure, post-treatment assessment available and no protocol violations deemed to affect both the primary tolerance endpoint (Evaluator global assessment) and the efficacy assessments (TEWL, corneometry).

Subjects with a protocol violation that is deemed to affect some, but not all, of the above 3 assessments will be part of the PP population, but their data will be excluded from the assessment at which the protocol violation occurred.

Violations that may lead to the exclusion of data for PP analysis include, but are not limited to, the following:

- Violation of inclusion or exclusion criteria at screening or baseline that may affect any of the above 3 assessments.
- Non-compliance with assigned treatment regimen.
- Use of prohibited treatment or medication before or during the study, which it is felt will affect any of the above 3 assessments.

Violations will be documented in the Population Definitions document. The content of this document will be agreed upon between the Biostatistician and Clinical Research Scientist or designee post database lock but prior to breaking of the study blind.

A PP analysis will be performed for the Evaluator global assessment, TEWL and corneometry if there is more than 10% difference in the number of subjects

evaluable in either of the treatment groups for the ITT and PP populations.

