*Lunchtime application must be at least 3 hours after previous sunscreen application

Subjects will not apply any sunscreen on the day of the facial peel procedure (Day 8), since they will remain at site until the evening (after 5 pm). On the morning of each visit, prior to arriving to the test site, subjects will be instructed to cleanse their face and not to apply any test product or sunscreen until after all measurements and assessments have been completed. Before leaving the site, subjects will undergo test product and/or sunscreen application under supervision. After leaving the site, subjects should apply the sunscreen a second time, but no sooner than 3 hours after the previous application.

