6.3.22. Supervised Test Product Application Post-Procedure

Subjects randomized to test product (Group I) will be instructed to apply the test product as per the labelled usage instructions immediately after the post-procedure, pre-treatment (baseline) assessments are complete. The Investigator or designee will oversee this initial product application. Group II will not apply any test product. Product application will be recorded on the eCRF and subject diary and must happen at least 30 minutes prior to any further instrumental measurements. The Investigator or designee involved in this step must not be involved in any assessments in order to protect the blind.

 GlaxoSmithKline	Document Name	Protocol 2017-01-08F 20 Day Cream.doc		
	Type	Version	Document Identifier	Effective Date
	eldo_controlled	0.0; CURRENT/Effective/Current/Reviewed	090032d580e2d8a6	07-Jun-2017 01:32:30
	Reason For Issue	Auto Issue		

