9.2. General Considerations

9.2.1. Definition of Analysis Populations

All randomized subjects will be included in the intent-to-treat (ITT) population. All subjects with at least one application of product in the test phase (i.e. test product for subjects in Group I or sunscreen for subjects in Group II) will be included in the Safety population.

Subjects will be considered eligible for a Per Protocol (PP) population if they were randomized, received at least one application of test product, had at least one post-procedure, post-treatment assessment available and were compliant with both test and washout products post-procedure. Other considerations for eligibility for the PP population including but not limited to use of concomitant medications will be detailed in the Statistical Analysis Plan prior to database unblinding.

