5.4 Missing Data Handling

Missing data will not be imputed. All data available for dropouts will be considered in analyses.

6 Demographics and Baseline Characteristics

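### The SAP's ITT set sits inside a Safety set whose product-use condition differs by arm, so subjects with the same early follow-up can be kept in Group 1 and dropped from Group 2

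*SAP*

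**What the plan says.** SAP 5.1 builds its sets in two steps. The Safety population is "All randomized subjects with at least one application of product in the test phase", where the qualifying product is the test cream in Group 1, "or sunscreen for subjects randomized not to receive test product (i.e. in Group 2)) will be included in the Safety population". The ITT set is then cut from it: "All subjects in the safety population with at least one post-baseline efficacy (TEWL or corneometry) assessment will be included in the ITT population". The SAP adds: "All efficacy analyses will be based on the ITT population".

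Protocol 9.2.1 has no such condition: "All randomized subjects will be included in the intent-to-treat (ITT) population". The protocol's own Safety set does use the arm-specific products. What the SAP adds is to carry that rule into ITT.

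SAP section 12 says that the population definitions were updated from the protocol. For ITT it gives only the new requirement of a post-baseline efficacy assessment, and otherwise says it clarifies which assessments use which set. It does not mention product use. SAP 5.4 says: "All data available for dropouts will be considered in analyses".

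On timing, protocol 6.3.22 has Group 1 apply the cream on Day 8 "immediately after the post-procedure, pre-treatment (baseline) assessments are complete. The Investigator or designee will oversee this initial product application". Note 12 to the Schedule of Events has Group 2 put nothing on the face at that step. The regimen text in protocol section 5 rules out sunscreen that day for both groups: "Subjects will not apply any sunscreen on the day of the facial peel procedure (Day 8"). Protocol 6.4.12 schedules the first supervised sunscreen after the peel as the last step of Visit 4 on Day 9.

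**The concern.** An ITT set should not depend on what a subject does with the assigned product, least of all through a condition that differs by arm. Here the qualifying product differs and so does the first moment at which it can be used. Subjects know whether they received cream, since only the evaluator is blinded. Leaving early or refusing product could therefore depend on the arm and on how the skin reacted to the peel.

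At stake is the between-group comparison of recovery in TEWL and Corneometer values, a stated secondary objective tested at each timepoint (SAP 8.2). The protocol expects barrier function to return to normal within 24 to 48 hours (section 3.4), so the early readings matter for these endpoints. The result would carry the ITT label without being the protocol's ITT analysis.

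**Working it through.** **1. The plan's own figure.** SAP section 4 gives SD 4, mean change 2.1, 30 subjects per group, two-sided alpha 0.05 and 80% power. As a within-group test of change from zero, the noncentrality is (2.1/4) × √30 = 2.88 on 29 df. The power is 79.4%, so the figure reproduces. A two-sample t-test with 30 per arm gives 51.6%, so the statement is a within-group one. It neither supports nor weakens this point, but it supplies the SD used in step 4. The planned loss is 1 − 60/80 = 25%, and 30/0.75 = 40 per arm.

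**2. The order of events (protocol 3.1, 6.3 and 6.4).**

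| Step | Group 1 | Group 2 |
|---|---|---|
| Day 8, 60 min: baseline | measured | measured |
| Day 8, straight after baseline | cream: enters Safety | nothing applied |
| Day 8, 180 and 360 min | measured | measured |
| Day 9, 24 h | measured | measured |
| Day 9, end of visit | cream and sunscreen | sunscreen: first scheduled entry to Safety |

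**3. Membership under SAP 5.1.**
- *Leaves after the Day 8 readings, with no sunscreen after the peel.* Group 1: in Safety and in ITT. Group 2: in neither, despite two post-baseline readings. The count is three if she leaves after the 24-hour reading but before the supervised sunscreen.
- *Misses Visit 4 but later applies sunscreen once, at home or at a visit.* Group 2: in ITT.
- *Never applies the cream but is measured.* Group 1: out of ITT at every timepoint, even if she uses sunscreen and attends every visit.
- *Leaves after baseline, before the cream.* Group 1: no post-baseline reading, so out whether or not product use is required.

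**4. Possible size for Group 2 leavers.** The documents do not say how many there would be. Assume 40 per arm, k subjects in each arm who leave after the Day 8 readings and before any sunscreen, SD 4, and leavers whose mean change differs from that of stayers by s, taken as 0.5 to 1 SD (2 to 4 g/m²/h). Group 1 keeps its leavers and Group 2 loses them, so the between-group difference moves by (k/40) × s. Its standard error is 4 × √(1/40 + 1/(40 − k)).

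| k | ITT, Group 1 v 2 | Share of Group 2 dropped | Shift, s = 2 | Shift, s = 4 | Shift in SEs, s = 4 |
|---|---|---|---|---|---|
| 0 | 40 v 40 | 0% | 0 | 0 | 0 |
| 1 | 40 v 39 | 2.5% | 0.05 | 0.10 | 0.11 |
| 2 | 40 v 38 | 5.0% | 0.10 | 0.20 | 0.22 |
| 5 | 40 v 35 | 12.5% | 0.25 | 0.50 | 0.54 |
| 10 | 40 v 30 | 25.0% | 0.50 | 1.00 | 1.04 |

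The last row puts every planned loss of one arm into this short window. It is an outer bound, not an expectation.

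**5. Which comparisons are touched.** Nothing is imputed (SAP 5.4) and tests are run timepoint by timepoint (SAP 8.2). A Group 2 leaver has no readings after 24 hours, so leaving her out cannot alter the 48-hour to 14-day instrumental comparisons.

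**The case against.** The strongest reply is that hardly anyone will be affected. Subjects stay on site until 5 PM on Day 8 and are asked back before 9 AM, so the main window is one night. The randomised retinoic acid peel study described in protocol 3.4 lost 2 of 52 subjects in a week. Spread evenly, that is 2/52/7 × 40 ≈ 0.2 of 40 subjects per night. It was a different peel, so this is only an order of magnitude, but it points to the top rows of the table. The Group 1 route is also unlikely, because a subject would have to refuse supervised cream at Visits 3 to 7 and every home application. The comparison is secondary and described as exploratory, and section 12 does disclose that the populations changed. All of this stands, and it limits the size of the problem. It does not make the definition even-handed.

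A reader might also infer more than the documents support:
- *That missing Visit 4 removes a Group 2 subject.* One later sunscreen application in the test phase keeps her in.
- *That the exclusion makes Group 2 look better.* The endpoint is change from a post-peel baseline. A strong early reactor could show a larger or a smaller fall, so the direction cannot be fixed in advance.
- *That the 20 planned losses measure the problem.* They cover both arms and the whole study after randomisation.
- *That SAP 5.1 flatly contradicts SAP 5.4.* One defines populations and the other deals with missing data. They are in tension, because data available for a dropout can go unused.
- *That the primary result turns on this ITT rule.* Table 9.3.1 uses the Safety population, and trial success depends only on the proportion in the test-product group.

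**Conclusion.** The point holds on the text. SAP 5.1 makes ITT membership depend on product use, with a different product and a different earliest time in each arm. This departs from protocol 9.2.1, and the reason given in section 12 does not cover it. Subjects with the same follow-up can be classified differently according to arm.

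The practical effect is probably small. With one or two leavers per arm, the early TEWL difference would shift by 0.05 to 0.20 g/m²/h, at most about 0.2 standard errors. That rests on an assumed 40/40 split, SD 4 and a leaver shift of 0.5 to 1 SD. The true number may be zero and the sign is unknown. For Group 2 leavers the instrumental effect stops at 24 hours. A Group 1 subject who never used the cream would be lost from all timepoints, but that case is improbable. The change is worth making because the fault is certain from the text and cheap to remove, not because a large bias has been shown.

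**What to change.** In SAP 5.1, define ITT as all randomised subjects with a baseline and at least one post-baseline TEWL or Corneometer reading, regardless of product use, analysed as randomised. Delete the condition of belonging to the Safety population. In section 12, state how this set differs from the protocol's all-randomised ITT. It remains narrower than the protocol's set, but only by the need for readings to analyse, and it keeps the post-baseline requirement that section 12 gives as the sponsor's reason.

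No common Day 8 starting point is needed once product use no longer matters. The Safety-based outputs, including Table 9.3.1 and the dermatologist and self-assessment score tables, are not changed. Counts in the other ITT tables (9.2.1.1 for demographics and 9.3.6 for satisfaction) would follow the new set.

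The cost is one definition, one derived flag and a sentence in section 12, agreed before unblinding. No new data are required.
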